Thus, the medium-dose lithium group (45mg/day of lithium aspartate) showed the most robust engagement of the PD therapeutic targets Nurr1 and SOD-1 but resulted in severe side effects in 1/3 of the patients. It is unclear why the medium-dose group would show more robust target engagement and more clinical side effects than the high-dose group despite having 35% lower serum lithium levels. We hypothesize that lithium may dissociate from the salt carrier aspartate more readily than from carbonate and/or cross cellular barriers more readily resulting in higher serum and/or intraneuronal “free lithium” levels at equivalent elemental lithium dosages of the two formulations. Because commercial lithium assays typically assess total, not free lithium levels, biological assays like PBMC Nurr1 expression represent a more objective way to compare dose-response relationships among different lithium formulations. This study’s findings of numerically higher magnitudes of PBMC Nurr1 and SOD1 mRNA expression associated with medium-dose lithium aspartate versus high-dose lithium carbonate support this hypothesis. In addition, one of the medium-dose lithium aspartate patients who withdrew due to side effects when receiving 45mg/day subsequently reported no side effects when receiving 30mg/day with a steady-state trough serum lithium level <0.1mmol/L. At 45mg/day of lithium aspartate, the highest predicted serum lithium level in this patient would be about 0.15mmol/L, which would be extremely unlikely to produce side effects if derived from lithium carbonate therapy. In support of this hypothesis, a recent study showed 10-100-fold disparate potencies of several different lithium formulations when assessed on an array of biological assays.

In addition to the blood-based therapeutic target results, the MRI FW results also supported medium-dose lithium aspartate as the most promising dose for further study. Out of the seven patients who received MRI scans at baseline and after 24-weeks of lithium therapy, six had reliable scan data at both timepoints (Figure 1).

Figure 1: Individual Patient Changes in FW after 24-weeks of High, Medium or Low-Dose Lithium Therapy

FW: free water, DMN-T: dorsomedial nucleus of the thalamus, nbM: nucleus basalis of Meynert, pSN: posterior substantia nigra

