## 5.0 Study Design\*

*5.1 Describe and explain the study design (e.g. case-control, cross-sectional, ethnographic, experimental, interventional, longitudinal, observational).*

Response:

We will enroll 15 additional PD patients within five months. Eligible patients will have PD for <4 years diagnosed by a movement disorder specialist (Drs. [name] or [name]), be 45-80 years old, have normal thyroid and renal function at the screening visit, have no previous exposure to lithium therapy, have no history of brain surgery, have no hx of brain imaging findings suggesting another neurological condition besides PD, have no use of tobacco or THC products for >1 year, have stable PD medications for >30 days without current need for adjustments in the investigator's opinion, and have stable psychiatric and diuretic medications for >60 days with no anticipated need for changes for at least 24 weeks.

All patients will receive medium-dose lithium aspartate therapy (30-45mg/day) for 24 weeks ensuring that the study will be completed within 12 months. The following dose titration will be used in order to minimize side effects: 10mg bid x 1 week, then 15mg bid x 1 week, then 20mg bid x 2 weeks, then 20mg qAM and 25mg qhs thereafter. Patients will be contacted weekly over the first 4-6 weeks to assess for side effects that are likely to be due to lithium, such as sedation, dizziness or confusion. If side effects occur and are bothersome to the patient, the dose will be decreased incrementally to a minimum of 30mg/day. Such a design will enable identification of the maximum tolerated dose for study in a future trial and maximize the number of patients receiving the most promising dose (45mg/day) identified in the previous pilot clinical trial. Blood-based biomarkers and MRIs will be assessed at baseline and 24 weeks.

The primary blood-based biomarker outcome measure will be change in PBMC Nurr1 mRNA expression from baseline to 24 weeks, which will be compared with the data from the three control PD patients from the pilot study using ANCOVA. PBMC mRNA expression will be assessed by quantitative real-time PCR using TaqMan probes to match the pilot study's methodology. Based on the

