22% standard deviation among the three control patients and the 540% treatment effect size for the primary outcome from the pilot study results, only two patients would be needed to detect a difference with 95% power at a 2-tailed alpha of 0.05. Secondary outcome measures will include 24-week changes in PBMC SOD-1 expression, PBMC pS9/total glycogen synthase kinase-3B (GSK-3B) and pThr308, pS473 and t-Akt and plasma interleukin-6 (IL-6) levels. Blood-based biomarkers will be assessed by [name]. Statistical analyses will be performed by [name].

The primary MRI outcomes will be 24-week MRI changes in DMN-T, nbM and pSN FW. Using ANCOVA, these outcomes will be compared with the known natural history of such changes in PD derived from the UF and PPMI longitudinal cohorts summarized in Table 1. In addition, secondary comparisons will be made between changes in these lithium-treated patients and age-matched and disease-duration-matched PD subsets from PPMI.

Exploratory clinical outcomes will include changes in Movement Disorder Society-Unified Parkinson's Disease Rating Scale (MDS-UPDRS) Part III (Motor Examination) with subjects in the "on" state, Montreal Cognitive Assessment (MoCA), Parkinson's Anxiety Scale, Geriatric Depression Scale-15, Fatigue Severity Scale, Insomnia Severity Index and Parkinson's Disease Questionnaire-8. Adverse events and medication compliance will be assessed at a three month phone call. Trough serum lithium and safety labs including HgA1C will be assessed at each visit. Because both baseline and on-treatment lithium levels will mostly be below the level of detection using conventional clinical laboratory services (i.e. Kaleida or Quest), these assays will be performed by the UB Chemistry Instrument Center under the direction of [name]. A protocol was developed by Drs. [name] and [name] for these assays for the pilot study that provided reliable results able to detect baseline lithium levels in all patients prior to initiation of lithium therapy.

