The diffusion-weighted imaging acquisition will be corrected for susceptibility-induced and eddy current/subject movement-induced distortions using a combination of the FSL tools topup and eddy. Next, the corrected diffusion weighted data will be processed with the free water elimination model implemented in DIPY (<https://dipy.org>) to obtain free water maps. Occipital FW changes will serve as an internal quality control since this ROI is known to have relatively small longitudinal FW changes over 1 year in PD. For example, data from PPMI showed 1-year pSN and occipital FW changes in PD to be 11.6% and 0.25%, respectively. In the lithium/PD pilot study, 24-week occipital FW changes ranged from -8% to 5% among the six patients with valid MRI scans. In the proposed study, patients with occipital FW changes of at least 14% from baseline to Week 24 will be excluded from the MRI outcome analyses as such changes would indicate an MRI acquisition anomaly at either visit.

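### The 14% occipital quality exclusion is stated for the lithium patients only, and it cannot expose a faulty baseline scan until after dosing.

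*Combined protocol and SAP*

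**What the plan says.** Section 5.1 gives the exclusion rule, "patients with occipital FW changes of at least 14% from baseline to Week 24 will be excluded from the MRI outcome analyses", and its reason: "as such changes would indicate an MRI acquisition anomaly at either visit". The rule is framed for the proposed study. The same section says of that study "We will enroll 15 additional PD patients within five months" and "All patients will receive medium-dose lithium aspartate therapy (30-45mg/day) for 24 weeks". There is no concurrent untreated arm for MRI.

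For the primary MRI outcomes, Section 5.1 says "these outcomes will be compared with the known natural history of such changes in PD derived from the UF and PPMI longitudinal cohorts", as summarised in Table 1, using ANCOVA. It adds that "secondary comparisons will be made between changes in these lithium-treated patients and age-matched and disease-duration-matched PD subsets from PPMI". No occipital rule is given for either comparator. Occipital FW does exist for PPMI, because the section reports that "data from PPMI showed 1-year pSN and occipital FW changes in PD to be 11.6% and 0.25%, respectively".

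On timing, Section 12.1 places the baseline MRI and Visit 2 in the same 21-day period following screening, with no stated order between them. Lithium is handed out at Visit 2. No acquisition check or repeat scan is described for the baseline MRI visit. The visual inspection in Section 5.1 concerns segmentation output and has no timing or rescan step. Section 19.3, on quality control of collected data, is answered as not applicable. Section 19.1 rules out imputation.

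On past loss, Section 4.1 reports that of seven pilot patients scanned twice, "six had reliable scan data at both timepoints". It gives no reason for the seventh. Section 5.1 gives the pilot's occipital changes as -8% to 5% in those six.

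**The concern.** Two separate things follow from how the rule is built.

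First, with an external control, any exclusion should operate alike on both sides. Here a patient with a large occipital shift leaves the lithium group, while nothing in the plan removes a PPMI patient with the same shift. The two distributions of FW change are then filtered differently, and the reader cannot tell how much of any difference in spread or mean comes from the filter.

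Second, the rule needs both scans. By the plan's own account the anomaly may sit at either visit, but a bad baseline comes to light only when the Week 24 scan has been processed. An off-drug baseline cannot be obtained at that point, and with no imputation the patient drops out of all three primary MRI outcomes. A check made before dosing could have saved that patient.

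**Working it through.** The plan states no MRI sample size, power or expected exclusion rate, so there is no figure of its own to reproduce on this point.

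**1. How many patients might the rule remove?** Inputs: the pilot occipital range of -8% to 5% in six patients, the 14% cut-off, and n = 15.
- The expected range of six normal values is 2.534 SD, so SD = 13/2.534 = 5.1 points, centred at the mid-range of -1.5.
- P(change ≥ 14) = P(Z ≥ 15.5/5.13) = 0.0013. P(change ≤ -14) = P(Z ≤ -12.5/5.13) = 0.0074. The sum is 0.0087.
- Expected exclusions are 15 × 0.0087 = 0.13, with a 12% chance of at least one.
- With an assumed SD of 8 or 10 points instead, the probability is about 8.5% or 17%, giving about 1.3 or 2.5 patients.

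**2. If the pilot's scan loss applied.** The rate is 1/7 = 14.3%, exact 95% CI 0.4% to 57.9%. Then 15 × 1/7 = 2.1 patients. This is loss from any cause at either visit.

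**3. What a loss of two would cost.** Inputs: Table 1 PPMI one-year means and SDs, pilot medium-dose mean changes (n = 2 each), two-sided 5%, two-sample t. The 95% half-width is t × SD × √(1/n + 1/N).

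| Region | Half-width, n=15 | n=13 | Power, n=15 | n=13 |
|---|---|---|---|---|
| pSN | 0.0301 | 0.0321 | 0.89 | 0.85 |
| DMN-T | 0.0162 | 0.0173 | 0.67 | 0.62 |
| nbM | 0.0221 | 0.0236 | 0.975 | 0.957 |

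**4. What one-sided trimming does to the lithium arm.** This was simulated under stated assumptions: between 1 in 15 and 1 in 7 scan pairs anomalous, an anomaly shift with mean zero and SD 15 to 25 percentage points common to the occipital and target regions, and a target-region SD of 15 points.
- Read as an absolute change, the rule removes 3% to 9% of pairs. The mean moves by about 0.1 point or less. The SD falls from 15.5 to 15.1 in the mildest case and from 17.7 to 15.2 in the strongest.
- Read as increases only, the mean falls by about 0.2 to 1.2 points. The text does not give the sign.
- The SD effect depends on the assumed 15 points. If the 11.6% and the Table 1 change of 0.018 describe the same PPMI sample, baseline pSN FW is 0.018/0.116 = 0.155, and the PPMI SD is 0.055/0.155 = 35% of baseline. With that spread the strongest case becomes √(35.5² + 90) = 36.7 falling to √(35.5² + 6) = 35.6, or about 3%. Here 90 = 17.74² - 15² and 6 = 15.19² - 15².

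**5. Can PPMI's mean be much inflated by unfiltered artefact?** Suppose 5% of PPMI pairs carried an occipital artefact of +14% to +30%. That alone would move mean occipital FW by 0.05 × 14 to 0.05 × 30, or 0.7 to 1.5 points. The reported change is 0.25%. If all of that 0.25% were artefact and carried equally into pSN, it would be 0.25/11.6 = 2% of the PPMI pSN rise, or 0.0025 × 0.155 = 0.0004. The standard error of the PPMI pSN mean is 0.055/√103 = 0.0054.

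**The case against.** A reader might infer that PPMI keeps its artefacts while lithium loses its own, so the comparison favours lithium. The documents do not support that. They do not say what quality control the PPMI and UF analyses applied, so all that can be said is that no matching rule is stated. The plan allows the anomaly at either visit. A spurious rise in FW at follow-up and one at baseline push the change in opposite directions, so there is no fixed sign. PPMI's small mean occipital change leaves little room for net inflation. The rule is also prespecified and uses a reference region rather than the outcome, which is good practice.

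A reader might also carry the pilot's loss of one in seven straight over as the cost of late detection. Nothing ties that loss to an occipital shift or to a baseline fault. The acquisition will also be newly optimised on a new scanner, so the rate may not transfer. An early check recovers baseline faults only.

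It is fair to add that the protocol does not forbid a repeat scan, and that its processing corrects for distortion and subject movement. However, correction sets no pass or fail criterion, and no step would trigger a repeat before dosing.

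Finally, a 14% limit chosen for 24-week pairs is not strictly the same filter on one-year pairs from other scanners. That stands, and is a reason to report the number removed on each side. It is not a reason to leave one side unfiltered.

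**Conclusion.** The concern holds in a limited form. The exclusion reaches lithium patients only, no counterpart is stated for PPMI although the occipital measure exists there, and a faulty baseline scan cannot be detected by this rule before treatment has begun.

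The first consequence is mainly a smaller SD in the lithium arm, by a few per cent to about 14% (17.7 to 15.2) depending on the assumed anomaly rate and spread. Under an absolute reading the mean hardly moves. No direction or size of bias in the mean is established.

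The second consequence is a loss of roughly 0 to 2 patients in 15, only part of it due to baseline faults. Two lost patients would cost about 2 to 6 points of power, if the pilot means from two patients are taken at face value. Both changes are worth making because they are cheap, and the baseline check must be settled before patients are dosed.

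**What to change.** **(a) Same rule on both sides.** State the occipital rule as an absolute change. Apply it to PPMI patient-level data wherever they are used. Both the ANCOVA and the matched subsets need such data. Report the number excluded on each side. Say plainly that the UF figures and the published Table 1 summaries cannot be filtered in this way, so any comparison resting on them stays one-sided.

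**(b) Baseline check before dosing.** Inspect the baseline diffusion series for motion and artefact during the scan session, and repeat a failed series before Visit 2. Keep the Week 24 rule as a back-stop.

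**Cost.** For (a), one filtering step and a slightly smaller PPMI reference sample. For (b), occasional extra scanner minutes, and scheduling the baseline MRI ahead of Visit 2 within the existing 21-day period. An in-session check does not require the full segmentation pipeline to be run before Visit 2.

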## 6.0 Study Intervention/Investigational Agent

1.1 Description: *Describe the study intervention and/or investigational agent (e.g., drug, device) that is being evaluated.*

Response:

Lithium aspartate (OTC dietary supplement).

6.1 *Drug/Device Handling: If the research involves drugs or device, describe your plans to store, handle, and administer those drugs or devices so that they will be used only on subjects and be used only by authorized investigators.*

- *If the control of the drugs or devices used in this protocol will be accomplished by following an established, approved organizational SOP (e.g., Research Pharmacy SOP for the Control of Investigational Drugs, etc.), please reference that SOP in this section.*

Response:

Lithium aspartate 5mg capsules will be purchased from e3 Pharmaceuticals, Inc. and manufactured in an NSF-certified facility in accordance with Good Manufacturing Practices (GMP). All study lithium will be stored at room temperature in a locked cabinet at the study site. All study lithium will be confirmed to not expire prior to being dispensed to study subjects.

6.2 *If the drug is investigational (has an IND) or the device has an IDE or a claim of abbreviated IDE (non-significant risk device), include the following information:*

- *Identify the holder of the IND/IDE/Abbreviated IDE.*
- *Explain procedures followed to comply with sponsor requirements for FDA regulated research for the following:*

FDA Regulation	Applicable to:		
	IND Studies	IDE studies	Abbreviated IDE studies
21 CFR 11	X	X	
21 CFR 54	X	X	
21 CFR 210	X		
21 CFR 211	X		
21 CFR 312	X		
21 CFR 812		X	X
21 CFR 820		X	

Response:

The FDA has issued IND exemption for lithium carbonate use in PD (IND #135530).

## 7.0 Local Number of Subjects

7.1 *Indicate the total number of subjects that will be enrolled or records that will be reviewed locally.*

Response: 15 additional patients (total of 34 including the 19 who have completed the study).

7.2 *If applicable, indicate how many subjects you expect to screen to reach your target sample (i.e. your screen failure rate).*

Response: 20

7.3 *Justify the feasibility of recruiting the proposed number of eligible subjects within the anticipated recruitment period. For example, how many potential subjects do you have access to? What percentage of those potential subjects do you need to recruit?*

Response:

Recruitment will occur from the PI's and [name] movement disorder clinic patients. The PI and [name] care for approximately 500 PD patients of which approximately 70% will be eligible. PD patients are anticipated to be highly interested in participating in this study since there currently are no disease-modifying therapies available for PD. Indeed, 18 PD patients have already voiced

interest in joining the study after being briefly informed of the study's rationale and procedures.

## 8.0 Inclusion and Exclusion Criteria\*

8.1 Describe the criteria that define who will be **included** in your final study sample.

NOTE: This may be done in bullet point fashion.

Response:

### Eligibility Criteria:

1. Diagnosed with PD according to the UK Brain Bank Criteria within the past four years with Hoehn & Yahr stage 1 or 2.
2. 45-80yo.
3. Stable PD medications for previous 30 days and no current need for changes in the opinion of the PI.
4. No formed visual hallucinations or delusions for previous year.
5. Screening MoCA  $\geq 20$ .
6. Never taken prescription or over-the-counter lithium.
7. Stable doses of antidepressants, antihypertensives, diuretics and non-steroidal anti-inflammatory medications (NSAIDs) for previous 60 days and no current need to adjust such medications.
8. No history of cardiac arrhythmias besides atrial fibrillation that is rate controlled.
9. No unstable cardiac, medical, neurologic or psychiatric condition in the opinion of the PI.
10. No current use of illicit drugs or current alcohol abuse in the opinion of the PI.
11. Normal thyroid stimulating hormone (TSH) level at screening visit.
12. Estimated renal glomerular filtration rate  $\geq 50$  at screening visit.
13. No history of receiving or planning to receive nilotinib or a glucagon-like peptide-1 agonist medication such as exenatide.
14. No use of tobacco, THC or CBD products for the previous year.
15. No history of brain surgery or possible need for brain surgery including deep brain stimulation (DBS) for at least 1-year in the opinion of the PI.
16. Women with child bearing potential will need a negative pregnancy test and not be nursing an infant at screening. Women with child bearing potential will need to report using barrier method or hormonal contraception.
17. Not enrolled in another clinical trial.
18. Willing and able to sign informed consent and follow study procedures.

8.2 Describe the criteria that define who will be **excluded** from your final study sample.

NOTE: This may be done in bullet point fashion.

Response:

See 8.1.

8.3 Indicate specifically whether you will include any of the following special populations in your study using the checkboxes below.

**NOTE: Members of special populations may not be targeted for enrollment in your study unless you indicate this in your inclusion criteria.**

Response:

- ☐ Adults unable to consent
- ☐ Individuals who are not yet adults (infants, children, teenagers)
- ☐ Pregnant women
- ☐ Prisoners

**8.4** *Indicate whether you will include non-English speaking individuals in your study. **Provide justification if you will exclude non-English speaking individuals.***

*In order to meet one of the primary ethical principles of equitable selection of subjects, non-English speaking individuals may **not** be routinely excluded from research as a matter of convenience.*

*In cases where the research is of therapeutic intent or is designed to investigate areas that would necessarily require certain populations who may not speak English, the researcher is required to make efforts to recruit and include non-English speaking individuals. However, there are studies in which it would be reasonable to limit subjects to those who speak English. Some examples include pilot studies, small unfunded studies with validated instruments not available in other languages, studies with numerous questionnaires, and some non-therapeutic studies which offer no direct benefit.*

Response:

Non-english speaking patients will not be enrolled as this is a pilot, proof of concept study and many of the PD questionnaires have not been translated out of English.

## **9.0 Vulnerable Populations\***

*If the research involves special populations that are considered vulnerable, **describe the safeguards included to protect their rights and welfare.***

*NOTE: You should refer to the appropriate checklists, referenced below, to ensure you have provided adequate detail regarding safeguards and protections. You do not, however, need to provide these checklists to the IRB.*

**9.1** *For research that involves **pregnant women**, safeguards include:  
NOTE CHECKLIST: Pregnant Women (HRP-412)*

Response:

- ☒ N/A: This research does not involve pregnant women.

- 9.2 For research that involves **neonates of uncertain viability or non-viable neonates**, safeguards include:  
NOTE CHECKLISTS: Non-Viable Neonates (HRP-413), or Neonates of Uncertain Viability (HRP-414)

Response:

- ☒ N/A: This research does not involve non-viable neonates or neonates of uncertain viability.

- 9.3 For research that involves **prisoners**, safeguards include:  
NOTE CHECKLIST: Prisoners (HRP-415)

Response:

- ☒ N/A: This research does not involve prisoners.

- 9.4 For research that involves **persons who have not attained the legal age for consent to treatments or procedures involved in the research (“children”)**, safeguards include:  
NOTE CHECKLIST: Children (HRP-416)

Response:

- ☒ N/A: This research does not involve persons who have not attained the legal age for consent to treatments or procedures (“children”).

- 9.5 For research that involves **cognitively impaired adults**, safeguards include:  
NOTE CHECKLIST: Cognitively Impaired Adults (HRP-417)

Response:

HRP-417 has been completed as is attached to this submission package.

- ☒ N/A: This research does not involve cognitively impaired adults.

- 9.6 Consider if other specifically targeted populations such as students, employees of a specific firm, or educationally or economically disadvantaged persons are vulnerable. **Provide information regarding their safeguards and protections, including safeguards to eliminate coercion or undue influence.**

Response:

